#### 1.4.2 - Clinical data - Pharmacokinetics

Resveratrol is well absorbed from the GI tract following oral administration, but has poor systemic bioavailability due to its rapid metabolism (68). Plasma pharmacokinetics for resveratrol have already been well characterised in a number of healthy volunteer studies. eliciting a maximal plasma concentration approximately 1 hour after oral dosing, with conjugates still detectable for up to 24 hours (69-71). Maximum plasma concentrations of resveratrol sulfate and glucuronide conjugates were up to 20-fold higher than those observed for the parent compound. The sulfate conjugates are thought to contribute to efficacy, as they are readily taken up into CRC cells via specific membrane transporters, where they are converted back into resveratrol, so increasing intracellular resveratrol levels at concentrations sufficient to exert anti-proliferative and pro-autophagic effects (72, 73). In addition to assessing plasma pharmacokinetics, several studies have analysed the distribution of resveratrol and its metabolites in colorectal target tissues at doses ranging from 5mg to 1g. The average resveratrol colorectal tissue concentrations were approximately 70-times higher than the plasma Cmax, with levels consistently higher in right- versus left-sided tissue (67). This may mean that resveratrol has potential for greater efficacy against tumours arising in the right side of the colon, which has similarly been observed for the adenoma preventive efficacy of aspirin (12).

#### 1.4.3 - Clinical data - Efficacy

We have recently undertaken a systematic review (awaiting submission for publication) assessing all trials and studies performed using resveratrol in humans, which specify the resveratrol dose and formulation used. To date, 133 individual trials have been reported with a cumulative enrolment of nearly 5000 participants and a further 36 studies have described additional analysis of samples or data from these trials.

Relatively few studies have been conducted specifically within a cancer setting, but a number of recent systematic reviews and meta-analyses have assessed the potential efficacy of resveratrol in other clinical settings that may have relevance for cancer. Resveratrol appears to consistently downregulate inflammation in a number of disease states including T2DM, metabolic syndrome and non-alcoholic fatty liver disease (NAFLD). Furthermore, the meta-analyses reveal consistent decreases in plasma glucose and insulin, and an improvement to insulin sensitivity. Mechanistically, prolonged inflammatory responses and high circulating glucose play an important role in promotion of the carcinogenic process. In the hyperglycaemic state, free glucose acts as a potent signalling intermediary, promoting formation of advanced glycation end-products and reactive oxygen species, in addition to stimulating pro-inflammatory and pro-proliferative signalling pathways (74) such as NFκB (75)

### 1.4.4 - Clinical data - Safety, drug interactions and choice of dose

Of the reported 133 clinical trials involving resveratrol, just over half (54%) involved patients with an underlying disease or pathology, with the remainder enrolling healthy participants. The near even split between healthy individuals and patients with a diagnosed pathology reflects a focus on health maintenance and prevention as well as using resveratrol as a potential treatment. Furthermore, the good safety profile of resveratrol means it has been possible to conduct many of the studies addressing PK, metabolism and bioavailability in healthy people. Resveratrol has been investigated in adults of all ages including elderly populations over 70 years. In our recent systematic review, we found that out of the 90 RCTs undertaken with resveratrol, 38 studies report zero side effects, 30 studies do not make any mention of side effects, and the remaining 22 studies provide detail for side effects, which are shown in Table

IRAS: 1005142 Page **29** of **109** 

6 (Appendix II). Of these 22 studies, 4 gave resveratrol in combination with standard of care drugs with known side effect profiles, but revealed no significant difference in side effects between groups. Of the remaining 18 studies, 11 of these administered resveratrol at or below our highest dose of 1 g/day, with 3 of these studies reporting that there were no significant differences in the number of participants experiencing side effects between the groups. Of the studies that do report side effects, the most common were dose-related and gastrointestinal in nature, comprising diarrhoea, constipation, nausea, abdominal cramps, vomiting, steatorrhoea, heartburn, reflux and bloating. Studies have shown that resveratrol is well tolerated at oncedaily doses of ≤1g, and one of the longest published trials in elderly Alzheimer's patients has demonstrated an excellent safety profile at doses of up to 1g taken twice daily for one year (76).

#### Drug interactions and use of concomitant medication.

Based on pharmacokinetic studies, resveratrol may theoretically interfere with phase I metabolism of certain drugs due to its inhibitory effects on cytochrome P450s (77). In theory, drugs relying on first pass metabolism for activation/efficacy (such as some statins, anti-fungals and anti-histamines) may be rendered less effective during co-administration of resveratrol. Two *in vivo* studies have suggested that there is an increased bleed risk when resveratrol is combined with the anti-clotting agent warfarin (78, 79) and as a precaution, patients on warfarin are not be eligible for COLO-PREVENT. All concomitant medication must be carefully reviewed by the clinical team prior to trial enrolment to ensure that participant safety is maintained, and efficacy of concomitant medication is not compromised.

#### Justification of dose

Resveratrol will be administered at a dose of 1 g, or 5 mg daily. Pre-clinical *in vivo* data have revealed that both these doses have preventive efficacy in a mouse model of CRC. Mechanistic studies have demonstrated a non-linear dose response for the effects of resveratrol on AMPK signalling and the induction of autophagy and senescence in adenoma cells, supporting further investigation of both doses. In our studies these doses have been administered safely in daily dosing regimens to patients and healthy volunteers and have been shown to alter molecular biomarkers relevant to CRC in human tissue, suggesting they may both have efficacy in trials, potentially through different mechanisms (62). It is not currently possible to determine which of these doses might be more effective for CRC prevention in humans, therefore both doses will be compared against placebo in the COLO-PREVENT sub-trial.

#### Lay Scientific Summary

One way of preventing bowel cancer is to take drugs or dietary supplements (this is called therapeutic prevention). Most bowel cancers develop over many years from a polyp. A polyp is a growth on the bowel wall; also known as an adenoma. Several clinical trials have shown that aspirin use reduces the risk of developing polyps and the drug metformin, which is used in patients to treat diabetes, can also reduce the number of polyps. We want to test whether combining aspirin with metformin is able to prevent more bowel polyps forming than aspirin alone. We will test this in 'high risk' patients taking part in the National Bowel Cancer Screening Programme (BCSP), who have already had polyps removed at the bowel camera test (colonoscopy). We are also keen to understand whether the dietary agent resveratrol which is found in red grapes, reduces the number of polyps formed. For this part of the trial we will test two doses against a placebo tablet in a way that neither patients nor medical staff know what treatment is being given (double blind). Patients already taking aspirin or metformin will be able to take part in the resveratrol sub-trial. The resveratrol sub-trial will be shorter and involve fewer

IRAS: 1005142 Page **30** of **109** 

patients than the main aspirin and metformin trial because we are just seeking an indication that resveratrol might protect against polyp recurrence; if the results are positive then they would provide justification to conduct a longer-term clinical trial in the future with the most effective dose of resveratrol.

Trial drugs will be given for 3 years in the main aspirin and metformin trial and 12 months in the resveratrol sub-trial, until patients have another planned BCSP colonoscopy, at which time the number and size of polyps will be measured. We will collect blood, faeces, urine and tiny samples of bowel tissue (biopsies) during the trial so that we can learn more about how the therapies work, as well as develop 'biomarker' tests to predict who will or won't respond to each therapy. We are particularly interested in examining the effects of the therapies on gut bacteria, which will be analysed using faecal samples. The expected benefit is that the therapies will reduce the number of polyps and therefore potentially the risk of developing a bowel cancer. A major advantage of metformin, aspirin and resveratrol is that they are safe, have few side-effects and are already widely used by people with diabetes, heart and/or stroke disease or as a dietary supplement.

#### 2. RATIONALE

#### 2.1 Hypothesis

**The Primary hypotheses** of this trial are:

- 1) The combination of metformin and aspirin affords greater preventive efficacy in high risk polyp patients compared to aspirin alone
- 2) Resveratrol prevents colorectal polyps in high risk individuals

#### 2.2 Need for a trial

It is estimated that the global burden of CRC will increase by 60% to more than 2.2 million new cases and 1.1 million deaths by 2030 (6). Prevention, through the use of safe and effective therapies, offers a largely untapped strategy for reducing the incidence and mortality due to CRC. Such therapies could be employed for primary prevention, but also in conjunction with screening/surveillance programmes for patients considered high risk due to the detection of premalignant colorectal polyps; the latter constitutes secondary prevention and may also serve to reduce the need for, or frequency of, surveillance colonoscopy.

Within the NHS Bowel Cancer Screening Programme, individuals classed as 'high risk' after an index colonoscopy have a high event rate over short periods of follow-up, with ~60% polyp recurrence within 12 months (11). Polyps detected post polypectomy may be due to both 'missed' and new lesions (11, 13). Evidence for *de novo* polyp growth comes from tandem colonoscopy studies in which there is as much as a 30% difference in polyp detection rate (PDR) at colonoscopy within three months of the index procedure compared with 12 months in high risk individuals (11, 13). Moreover, the occurrence of post-colonoscopy CRC, particularly right-sided tumours, is increasingly being recognised, even for those engaged in high quality

IRAS: 1005142 Page **31** of **109** 

surveillance programmes (80-82). These facts highlight the opportunity for improvement by combining preventive therapies with endoscopic interventions in this population.

There is compelling evidence from epidemiology data and randomised clinical trials that aspirin can prevent colorectal cancer and polyps, and that this protection translates to reduced CRC associated mortality (9, 26, 83). However, aspirin does not work for everyone; therefore, there is a need to identify effective adjuncts and/or alternatives to aspirin, to expand the proportion of patients who can experience a net benefit from preventive therapy. The weight of evidence for efficacy of metformin in this context, coupled with excellent safety profiles, places this drug at the top of the pipeline for testing in combination. It is striking that despite the strong case for using aspirin for CRC prevention in high risk groups, such as those with Lynch syndrome (32), implementation has been challenging due to limited awareness among potential prescribers and concerns over the safety of higher doses (84). In COLO-PREVENT we are adopting aspirin as standard of care in the main trial and we anticipate this action will help raise awareness among healthcare professionals and the public, increase the acceptability and alleviate concerns over safety, which in turn will aid wider implementation, leading to more routine use.

Gaining proof of concept for clinical efficacy is a considerable barrier to translating promising preventive therapies to full phase 3 clinical evaluation. Therefore, a novel feature of the COLO-PREVENT platform is the incorporation of signal-seeking arms, which will allow earlier phase testing of interventions for which there is not yet sufficient evidence to justify a large phase 3 clinical trial. Efficacy will be evaluated in a smaller number of patients over a shorter period, at which stage a 'go/no-go' decision can be made regarding continued assessment within the COLO-PREVENT platform. The Signal-Seeking sub-trial provides a conduit for linking laboratory work with phase 3 assessment, in a unique package. We have selected resveratrol as the prime candidate for the sub-trial; there is a body of preclinical evidence supporting the potential of resveratrol as a preventive therapy for CRC aligned to promising pharmacodynamic biomarker changes in target tissues from pre-surgical window trials (62, 67, 85). Efficacy testing in a clinical setting is the next logical step.

#### 2.3 Exploratory studies

Exploratory translational work will centre on the hypothesis that metabolic status and dietary factors influence the effectiveness of aspirin, metformin and resveratrol, such that individuals with poor metabolic health may experience greater benefit. **Further exploratory analyses** will investigate whether metformin and aspirin have additive effects on molecular targets associated with pathways modulated by both drugs and ascertain whether candidate pharmacodynamic biomarkers of resveratrol efficacy, previously identified in our preclinical studies, translate to the clinic. We will also examine whether correlations exist between plasma concentrations and/or metabolite profiles of resveratrol and metformin and efficacy and evaluate the role of the gut microbiome in predicting and mediating the effects of the three interventions.

1) We will test the hypothesis that metabolic status and dietary factors influence the effectiveness of aspirin, metformin and resveratrol, such that individuals with poor metabolic health may experience greater benefit. To this end we will characterise the metabolic status and dietary patterns of participants at baseline, middle and end of both trials and examine associations with efficacy for each intervention. This will include determination of BMI, waist circumference and analysis of fasting glucose, insulin (HOMA), HbA1c, triglycerides,

IRAS: 1005142 Page **32** of **109** 

cholesterol, IGFBP-3, and free IGFI, plus completion of EPIC Food Frequency Questionnaires (FFQs) and estimation of dietary fat content (86, 87).

- 2) We will examine the hypothesis that plasma drug concentrations and/or the metabolite profile correlate with efficacy for metformin and resveratrol. This will involve measurement of metformin blood concentrations and determining the plasma metabolite profile for resveratrol, including the proportion of human and bacteria-derived species since the pattern of resveratrol metabolites may influence, and therefore correlate with, efficacy.
- 3) We will test the hypothesis that combining aspirin and metformin leads to additive efficacy due to overlapping mechanisms of action and this can be detected through the measurement of pharmacodynamic biomarkers. This is a pilot that will be conducted with samples from 20% of randomly selected patients to ascertain if the drugs are modulating proposed targets. If the results suggest additive activity then the data will be used to inform the powering of a larger analysis in which correlations with preventive efficacy on polyp recurrence can also be explored. We will focus on markers of AMPK activation and/or mTOR inhibition in normal rectal tissue of patients that received aspirin, as well as the NF-kB pathway. Apoptosis will be quantified as a functional endpoint for the effects of aspirin and metformin on these pathways. Therapy-associated differences will be investigated for the three biomarkers in normal tissue of all designated patients by comparing between trial arms. Biomarker changes in adenomas will be determined for the proportion of patients presenting with a recurring polyp at 3 years by comparing results pre- and post-intervention and across groups.
- 4) We will test the hypothesis that resveratrol pharmacodynamic biomarkers identified in our preclinical studies as correlating with efficacy in mice, translate to the clinic. Specifically, NQO1 protein expression and protein carbonyl levels in normal tissue, plus Ki67 labelling index in both normal and adenoma tissue (62, 67), and plasma MLX and CIDEB protein concentrations will be analysed across treatment groups and over time in the resveratrol signal-seeking sub-trial and associations with efficacy examined.
- 5) We propose that the interventions used in both trials of the COLO-PREVENT platform favourably alter the gut microbiome in a way that might contribute to efficacy. We will test this hypothesis by first comparing the baseline microbiome of the high risk trial participants to our current data sets from BCSP patients, to confirm and refine our findings of a characteristic microbiome within these individuals. We will then ascertain the development of systematic changes in the microbiome caused by aspirin, metformin and resveratrol and explore the potential contribution of these therapy-induced microbiome changes to any efficacy observed, in terms of reducing polyp recurrence. We will also conduct metabolomic and proteomic analysis of plasma and colorectal tissue to identify profiles associated with baseline microbiome composition or therapy-related changes to the microbiome. All research faecal samples will be obtained using faecal immunochemical test (FIT) kits and bacterial populations will be assessed by next generation sequencing of the 16S rRNA V4 region. Residual extracted DNA from the stool will be saved and subsequently tested for specific oncomicrobes or toxin genes should important new data emerge within the timeframe of the trial.

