#### 4. TRIAL DESIGN

Both the main trial and the embedded resveratrol sub-trial are multi-centre, randomised, parallel, controlled interventional prevention trials. The main phase III trial will recruit 862 participants and the phase II signal-seeking sub-trial will recruit 477 participants; giving a combined total of 1339 participants.

For the open-label main trial, patients will be randomised to receive either aspirin (control group) or aspirin + metformin (intervention) daily for 3 years. A low dose of aspirin at 75mg once daily will be the backbone standard treatment in both arms, with those randomised to the interventional arm receiving metformin at a dose of 500mg twice a day. In the multi-arm, double-blinded, signal-seeking sub-trial, patients will be randomised to receive 5mg of resveratrol, or 1g of resveratrol, or placebo, once daily for 1 year.

The patient population will be adults aged 50-71 years for the main trial and 50-74 years for the sub-trial, who are identified as high risk for colorectal cancer at their **first complete screening episode** within the Bowel Cancer Screening Programme (BCSP). This includes individuals with 'high risk' findings according to the BCSP definitions (see Figure 2) or a large (≥20mm) non-pedunculated colorectal polyp (LNPCP). For patients with an LNPCP, these will be eligible for recruitment after their first complete screening episode if the resection is a histological R0 *en block* excision. Where there is piecemeal resection of an LNPCP, patients will be eligible only if their **2**nd **site check** is a **full clearance colonoscopy**; in these cases patients would become eligible after completion of this procedure (see Figure 2). For full inclusion/exclusion criteria see section 6.

We aim to assess the efficacy, safety and mechanisms of these potentially preventive treatments within this population. The primary endpoint is polyp number (MPP), secondary endpoints include polyp detection rate (PDR), advanced polyps, polyp subtype and location, adverse events and compliance. Research endpoints will focus on the association between metabolic status and treatment efficacy, assessment of pharmacodynamics biomarkers and role of the gut microbiome in predicting and mediating the effects of the three therapies.

IRAS: 1005142 Page **39** of **109** 

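### Section 2.3 promises tests of aspirin's effect modifiers, of aspirin–metformin additivity and of aspirin-caused microbiome change, but only metformin is randomised in the main trial, so none of the three has a randomised test

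*Protocol*

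**What the plan says.** Section 4 of the protocol sets up two main-trial arms: "patients will be randomised to receive either aspirin (control group) or aspirin + metformin (intervention) daily for 3 years". It adds: "A low dose of aspirin at 75mg once daily will be the backbone standard treatment in both arms". No main-trial participant is assigned to no aspirin, or to metformin without aspirin.

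Section 2.3 then lists exploratory aims that name aspirin as an agent whose own effect will be studied:

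- Item 1: "We will test the hypothesis that metabolic status and dietary factors influence the effectiveness of aspirin, metformin and resveratrol".
- Item 3: "We will test the hypothesis that combining aspirin and metformin leads to additive efficacy due to overlapping mechanisms of action". The method for normal tissue is: "Therapy-associated differences will be investigated for the three biomarkers in normal tissue of all designated patients by comparing between trial arms". The consequence is: "If the results suggest additive activity then the data will be used to inform the powering of a larger analysis".
- Item 5: the investigators will "ascertain the development of systematic changes in the microbiome caused by aspirin, metformin and resveratrol".

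Section 11.3.4 leaves detail to a separate biomarker SAP. It does fix that each marker is first assessed as prognostic for polyp number and then through a treatment-by-marker interaction, for the treatment comparisons that the hypotheses specify. Those hypotheses are the ones in section 2.3.

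**The concern.** Each of the three aims needs a contrast that the main trial does not contain. Effect modification for aspirin needs variation in aspirin. Additivity needs the effect of metformin without aspirin and the effect of aspirin itself. A claim that aspirin caused a change needs a comparable group without aspirin.

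No analysis method in a later SAP can supply a missing arm, so the statement has to be corrected in the protocol. What is at stake is interpretation. An association between metabolic health and polyp number among aspirin takers could be read as predicting who benefits from aspirin. A trend over time could be read as an aspirin effect, and an ordinary effect of metformin on top of aspirin could be read as additivity. The last of these is also what section 2.3 would use when planning a larger tissue analysis.

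**Working it through.** **Inputs.** Section 11.1 gives an assumed untreated mean polyp number per participant (MPP) of 1.2 at 3 years, a 22% reduction with aspirin, and a further 30% reduction with the combination. Sections 4 and 7.3 give the arms and the 1:1 randomisation.

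**The plan's own figures.** 1.2 × 0.78 = 0.936, stated as 0.94. 0.94 × 0.70 = 0.658, stated as 0.66. Reading the over-dispersion of 2.0 as variance/mean = 2, the sample size per arm is (1.960 + 0.842)² × (2/0.94 + 2/0.66) / [ln(0.66/0.94)]² = 323.7, against a stated 323. That calculation uses only the two populated arms, so nothing below touches it.

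**Additivity (item 3).** Write the four cell means as μ₀ (neither drug), μ_A, μ_M and μ_AM. The main trial observes only μ_A and μ_AM. Taking μ₀ = 1.2, μ_A = 0.94 and μ_AM = 0.66, three quite different truths give the same two-arm result:

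| Truth about metformin alone | Formula for μ_M | Value |
|---|---|---|
| Effects add on the difference scale | μ₀ − (μ_A − μ_AM) = 1.2 − 0.28 | 0.92 |
| Effects multiply | μ₀ × μ_AM/μ_A = 1.2 × 0.66/0.94 | 0.84 |
| Metformin does nothing without aspirin | μ₀ | 1.2 |

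μ_M is not measured in the main trial, and μ₀ is assumed. The same argument holds with a tissue marker in place of MPP.

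Before/after data do not fill the gap. Table 1 and section 7.2.1 schedule rectal biopsies of normal tissue only at the exit colonoscopy, and they are optional. Adenomas do get a before/after comparison, but only in participants whose polyps recur and without an aspirin-free group. The pilot covers 20% of participants, 0.20 × 862 ≈ 172, which is an upper limit for the normal-tissue assays because biopsy is optional.

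**Modifiers of aspirin's effect (item 1).** Let A and M indicate aspirin and metformin, and X a baseline marker:

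log E(polyps) = β₀ + β_A·A + β_M·M + β_X·X + β_AX·A·X + β_MX·M·X.

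By assignment A = 1 for every main-trial participant, so this becomes (β₀ + β_A) + β_M·M + (β_X + β_AX)·X + β_MX·M·X. The aspirin-by-marker term β_AX is merged with the prognostic slope β_X and cannot be separated from it. Only β_MX, the modifier of adding metformin to aspirin, is estimable.

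**Microbiome (item 5).** Section 3.7 gives faecal samples at weeks 0, 52 and 154. Change from week 0 in the aspirin arm combines any aspirin effect with everything else that changes over that time. The difference between arms isolates metformin added to aspirin.

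**The sub-trial.** Section 6.1 permits aspirin there, and section 7.3 balances aspirin or metformin use across the resveratrol and placebo arms, but neither drug is randomised. Section 1.1 offers the sub-trial to people who already use, cannot take or do not want the main-trial drugs. Treatment lasts one year. Comparing its aspirin users or non-users with main-trial participants is therefore confounded by indication and by population.

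**The case against.** The strongest reply is that the aims are not empty. In everyday usage, additive can mean that metformin adds something to aspirin. The between-arm comparison answers that, and it matches the first primary hypothesis in section 2.1. Adenomas get a before/after comparison. Sub-trial participants not taking aspirin give faecal samples at weeks 0 and 52, so an aspirin-free group exists over the first year. Section 11.3.4 already separates prognostic from interaction analyses. The larger analysis is not automatic, because the pilot result only informs its powering. All of this is labelled exploratory, and aspirin in both arms is a deliberate standard-of-care choice.

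All of that stands, and it rules out some stronger readings. A reader might infer that none of these questions can be answered at all, or that no aspirin-free comparison exists anywhere in the platform. The documents do not support either: incremental benefit is testable, and descriptive comparisons are available. A reader might also infer that the week 0 faecal sample is distorted by recovery from the index colonoscopy, but nothing in the protocol describes such an effect. Nor does the text oblige anyone to report a prognostic association as a predictor of aspirin benefit.

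The reply does not supply a randomised contrast for aspirin. Item 3 attributes additive efficacy to overlapping mechanisms, which goes beyond asking whether metformin adds anything. Items 1 and 5 name aspirin as the agent whose effect is modified or causal.

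**Conclusion.** Section 2.3 claims a property that the design does not have. The main trial estimates the effect of adding metformin to aspirin, and what modifies that effect. It gives no randomised test of modifiers of aspirin's effectiveness, of strict additivity, or of aspirin-caused microbiome change.

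The additivity gap is wide: metformin-alone means from 0.84 to 1.2 are all compatible with the planned result. This illustration rests on the protocol's assumed untreated mean of 1.2, but the identifiability conclusion needs only that two of the four cells are unfilled in the main trial.

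The resveratrol parts of these aims are unaffected. The metformin parts hold as effects on top of aspirin. The aims are exploratory, and the primary analysis and sample size do not change.

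**What to change.** - **Section 2.3, item 3:** replace the additive efficacy and additive activity wording with *incremental effect of metformin in aspirin-treated participants*. Make the between-arm marker difference in normal tissue, which is already planned, the criterion that informs the larger analysis.
- **Section 2.3, items 1 and 5, and the predictive analyses in section 11.3.4:** limit effect-modification and causal claims to metformin added to aspirin and to resveratrol versus placebo. Label aspirin-specific associations as prognostic. Label before/after changes on aspirin, and comparisons with sub-trial non-users, as descriptive and non-randomised.
- **Biomarker SAP:** carry the same wording through.

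The cost is text only, with no new participants, samples or assays. The downside is that the trial claims less about aspirin.
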